### 1.1 Objectives

Oral cancers will be biopsied by [name], [name], [name] and [name] and [name]. Precancerous oral lesions will be biopsied by [name]. For oral cancer/precancer patients biopsied at an outside institution and referred to Rutgers/University Hospital for care, outside H&E slides and unstained specimens for PDPN staining will be requested. [name] and [name] will evaluate tumor pathology, cell morphology, and PDPN expression in these patient samples. [name] will evaluate PDPN expression and MASL sensitivity from primary cultures of these cells. Study clinicians will evaluate oral cavity and health of their respective patients before and after MASL treatment. [name], [name], [name], [name], [name] or [name] will administer MASL dosage, evaluate any effects on oral structure and epithelium, and perform clinically indicated resection or biopsy to obtain specimen after treatment. [name], [name], [name], [name], [name] or [name] along with [name] and [name] will measure overall health before and after administration, and evaluate potential allergic reaction to MASL and respond to any unlikely scenarios. [name], [name] and [name] will evaluate pathology, cell morphology, and PDPN expression in these samples. We will determine if MASL treatment can decrease PDPN expression and normalize cell morphology in oral cancers and precancerous lesions.

Thus, primary, secondary, and tertiary objectives are as follows:

- a. Primary Objective: To evaluate and compare the morphology and podoplanin (PDPN) expression of cells included in the oral lesion initial biopsy to normal oral squamous epithelial cells (OSCCs).
- b. Secondary Objective: To evaluate and compare the PDPN expression of cells included in the resected oral lesion to normal oral squamous epithelial cells.
- c. Tertiary Objective: To evaluate and compare the morphology of cells included in the resected oral lesion to normal oral squamous epithelial cells.

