### 1.3 Primary, Secondary, and Tertiary Endpoints

Endpoints will be determined by cell morphology and PDPN expression examined by IHC. This work will be performed as an integral part of the study. The protocols rely on standard staining protocols to visual cells and PDPN expression with an approved antibody (D2-40). We have experience with this approach as previously described [56].

Our primary endpoint will be measured from patient biopsy material. We will compare the morphology and PDPN expression of cells included in the oral lesion to normal oral squamous epithelial cells. Patients eligible for the study will provide samples with lesion cells that are determined to be OSCC and express more PDPN than normal cells from the same sample specimen. In addition, these OSCC cells will express PDPN levels that are equivalent or greater than PDPN levels expressed by lymphatic endothelial cells (LECs) from the same specimen. Although this may be considered inclusion criteria, it is also an endpoint since these data will confirm that PDPN expression is increased in OSCC cells in our patient population. PDPN expression will be assessed by IHC for this endpoint since it can be used to qualitatively and quantitatively assess PDPN expression and be accomplished along with standard evaluations used for best care practice.

Our secondary endpoint will be measured from patient resection or second biopsy material. We will compare the PDPN expression of cells included in the oral lesion to normal oral squamous epithelial cells. Our secondary endpoint will be met if MASL treated OSCC cells express less PDPN than normal cells from the same sample specimen. In addition, these OSCC cells will express PDPN levels that are lower than PDPN levels expressed by lymphatic endothelial cells (LECs) from the same specimen. Our secondary endpoint will also require that the degree of PDPN expression decrease occurring after MASL administration is greater than any PDPN expression decrease observed after placebo administration. This comparison will be analyzed by t-test to achieve a p value less than 0.05.

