[name] and [name] will evaluate PDPN expression and cell morphology by IHC from formaldehyde fixed section of these samples. Surgical specimens will be fixed in 10% formalin in PBS, paraffin embedded, sectioned (4 microns), and processed for hematoxylin/eosin staining and immunohistochemistry D2-40 monoclonal antibody (Dako) to detect PDPN as described [56]. Paraffin-fixed specimens will be prepared by the local oral pathology laboratories at the University Hospital in Newark, NJ as part of the diagnostic histopathology. Routine pathology reports generated during patient care will also be examined to verify the tumor grade and nature of these specimens. Data will be examined by [name] and [name] in a blinded manner with coded labels such that they will not know whether the specimens are from MASL or placebo treated patients.

In addition to IHC analysis, [name] will establish primary cell cultures from these samples. He will evaluate cell morphology, assay PDPN expression by Western blotting, and evaluate the effects of MASL on the growth and migration of these cells by standard growth and motility assays [57]. This work will be performed at the Science Center in Stratford, NJ. Results from these studies will be used to elucidate understand how OSCC cells respond to MASL. However, these cell culture data will not be used as eligibility criteria since these assays may not be accomplished in a time frame consistent with treatment plans. The IHC analysis can be completed within 4 days. Therefore, this testing will not delay any subsequent treatment plans or options.

Patients with OSCC cells that express robust levels of PDPN will be considered for treatment. Robust levels of PDPN will be defined as greater than normal cells and equivalent or greater than PDPN levels expressed by lymphatic endothelial cells (LECs) from the same sample specimen. Patients that meet the eligibility criteria will be enrolled in the treatment phase of this study. Study clinicians ([name], [name], [name], [name], [name] or [name]) will administer MASL or placebo to enrolled subject. Patients will be given a lozenge (troche)with or without MASL added to achieve a final dosage of 100 mg per adult. Clinicians administering the lozenge and [name] are not blinded to the type of the lozenge; however, this information is not available to the pathologist who evaluates tumor pathology, cell morphology, and PDPN expression in the patient samples.

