### **3.3 Sample Size Justification**

We will recruit up to 10 patients for MASL treatment and 10 patients for placebo treatment to attempt a p value of less than 0.05 based on a difference of 40% with respect to Podoplanin expression and MASL sensitivity. Patients will be selected for treatment with MASL versus placebo by 1:1 randomization.

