#### **3.5.1 Inclusion Criteria**

- 1.) Males and females of at least 18 years of age who are able to give consent.
- 2.) Smokers and non-smokers.
- 3.) Persons with white or red spots and/or lesions suspected or found to be oral cancer or precancer on the inner surface of the mouth.
- 4.) Oral lesions will be classified as OSCC or leukoplakia including, proliferative verrucous leukoplakia, conventional erythroplakia, suspect oral papillomas, or oral lichen planus. Only patients with such histologically confirmed diagnoses will be considered for inclusion.
- 5.) patients will be considered for inclusion at any stage of disease progression.
- 6.) Patients will be considered for inclusion if a subsequent biopsy or surgical resection are planned as part of their best care treatment.
- 7.) Patients with previously diagnosed oral cancer/precancer who present to the study clinicians for definitive surgical care, consent to participate, and meet the criteria for enrolment.
- 8.) Patients will have an Eastern Cooperative Oncology Group performance status of 0 or 1.
- 9.) Patients will display normal organ function as evidenced by standard laboratory blood tests including liver enzymes and creatine.
- 10.) Patients will not present evidence of comorbidities including ongoing or active infection, unstable illness, or medical conditions.

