## Study Design Flowchart

Biopsies taken from patients will be examined by immunohistochemistry (IHC). Patients with lesions with high PDPN expression who meet the eligibility criteria for the trial phase will be offered MASL treatment before resection or second biopsy as determined by best care practice. Surgical specimens will then be examined by IHC to examine the effects of MASL on PDPN expression and cell morphology. Our hypothesis predicts that MASL will reduce PDPN expression and normalize the morphology of oral squamous carcinoma cells.

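### The planned post-treatment procedure (resection or second biopsy) is known before treatment but is used neither in the 1:1 allocation nor in the PDPN t-test, which costs precision in a 20-patient trial

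*Protocol*

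**What the plan says.** Protocol section 1.3 takes the two PDPN readings from different kinds of material. For the first, "Our primary endpoint will be measured from patient biopsy material". For the later one, "Our secondary endpoint will be measured from patient resection or second biopsy material". The secondary objective in section 1.1 mentions only the resected lesion, so the two sections do not quite agree on the later specimen.

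Clinical care decides which procedure a patient has. The Study Design Flowchart says that eligible patients "will be offered MASL treatment before resection or second biopsy as determined by best care practice". The choice is made early: criterion 6 in section 3.5.1 reads "Patients will be considered for inclusion if a subsequent biopsy or surgical resection are planned as part of their best care treatment", and the Schedule of Events places the planning of that procedure ahead of the treatment phase.

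The between-arm requirement in section 1.3 is that "the degree of PDPN expression decrease occurring after MASL administration is greater than any PDPN expression decrease observed after placebo administration", tested by t-test at p < 0.05. On allocation, section 3.3 says "Patients will be selected for treatment with MASL versus placebo by 1:1 randomization", for up to 10 patients per arm; section 3.5.3 repeats this. Neither mentions a stratification factor. Section 5 lists means, standard errors, t-test and ANOVA.

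**The concern.** A biopsy-to-resection change and a biopsy-to-biopsy change may differ for reasons unrelated to the drug, because a resection offers more of the lesion to read. The type of procedure may also go with the type and stage of lesion. Section 2 reports elevated PDPN in over 30% of precancers and over 60% of oral cancers, and in about 50% of T1/T2 and 75% of T3/T4 cancers. Section 3.5.1 admits both precancer and cancer, at any stage.

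If specimen type affects the measured decrease, a t-test that ignores it leaves that variation in the error term. With at most 20 patients and only one MASL-versus-placebo test of PDPN decrease, there is little precision to spare. A factor known before treatment can be balanced by design. Once patients have been randomised, that option is gone.

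**Working it through.** **Inputs from the protocol.** Up to 10 per arm, a 40% difference and p < 0.05 (section 3.3); t-test (section 1.3).

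**Assumptions, because the protocol gives no figure.** The 40% is read as 40 points of PDPN decrease and the test is two-sided. The within-procedure SD is 30 points. Either 10 or 4 of the 20 patients have a resection. Specimen type shifts the measured decrease by 20, 30 or 45 points (0.67, 1 or 1.5 SD).

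**1. The plan's own figure.** Ten per arm cannot be confirmed or refuted without an SD and a power. With SD 30, the noncentrality is 40 / (30 × √(2/10)) = 40 / 13.42 = 2.98 on 18 df, which gives power of 80.5%. SD 30 is therefore roughly the value at which the stated size delivers 80%. Without any specimen effect, power would be 56% at SD 40 and 40% at SD 50.

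**2. Power when the split is ignored.** With a share p of resections and a shift s, the SD seen by the t-test is about √(30² + p(1 − p)s²). For p = 0.5:

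- s = 20: √(900 + 100) = 31.6
- s = 30: √(900 + 225) = 33.5
- s = 45: √(900 + 506) = 37.5

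The table shows simulated power under simple randomisation into arms of 10 with the unadjusted t-test, against stratified allocation (equal within each stratum) with procedure in the model (17 df).

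| Shift (points) | t-test, 10 of 20 resected | t-test, 4 of 20 resected | Stratified and adjusted, either split |
|---|---|---|---|
| 0 | 80% | 80% | 80% |
| 20 | 76% | 77% to 78% | 80% |
| 30 | 71% | 74% | 80% |
| 45 | 60% to 61% | 67% | 80% |

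Adjustment without stratification gives about 77% to 78% at every shift, because chance imbalance then costs some information. The two halves of the fix belong together.

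**3. Type I error.** Averaged over the randomisation, the unadjusted t-test rejects a true null in 5.0% to 5.1% of trials.

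**4. A trial that happens to be imbalanced.** The number of resections in one arm is hypergeometric. With 10 of 20 resected, the chance of 6 v 4 or worse is 0.656, and of 7 v 3 or worse 0.179. With 4 of 20, the chance that the arms differ by 4 is 0.087. The arm difference moves by shift × (difference in counts) / 10. At a 20-point shift, 6 v 4 moves it by 20 × 2 / 10 = 4 points and 7 v 3 by 20 × 4 / 10 = 8 points, one fifth of the 40-point target. Given an exact 7 v 3 split, the false-positive rate is about 7% at a 20-point shift and 9% at a 30-point shift. Given 5 v 5, it is about 4% and 3%. These average back to 5%.

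**The case against.** A reader might infer that specimen type will systematically pass for a drug effect. The documents do not support this. Allocation is randomised, the procedure is planned before treatment, and step 3 shows an overall error rate near 5%. There is one route to real bias. The clinicians who give the lozenge "are not blinded to the type of the lozenge", and section 1.1 has the treating clinicians also "perform clinically indicated resection or biopsy to obtain specimen after treatment". But nothing in the protocol suggests that arm would influence the choice of procedure.

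Other objections have weight:

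- No passage says that resections and biopsies give different PDPN readings. Section 1.3 compares lesion cells with normal and lymphatic endothelial cells of the same specimen, which may absorb part of a specimen effect. However, the protocol does not say that the between-arm decrease is scaled to them.
- The split may be small. Sections 1.3 and 3 describe treated patients as having OSCC cells, and if nearly all go to resection there is little to gain. Section 3.5.1 also admits precancerous lesions, so the share is unknown.
- A covariate could be added in a statistical analysis plan that is not at hand, and section 5 already names ANOVA. But section 1.3 commits to a t-test, and an analysis plan cannot stratify an allocation already made.
- Small fixed blocks within strata would let unblinded recruiting clinicians guess the next assignment. This stands, and it shapes the fix.

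**Conclusion.** The point holds as one of efficiency. A factor that is known before treatment and plausibly related to the outcome is left out of both the allocation and the only between-arm PDPN comparison. The loss is about 4 power points at a 20-point shift, 9 at 30 points and 20 at 45 points if half the patients have a resection. It is about 3, 6 and 13 points with 4 of 20. If specimen type has no effect, nothing is lost.

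Beyond power, a chance-imbalanced trial would give a shifted estimate. A shift of 8 points or more has probability 0.18 under the 20-point, half-resection assumption. This is chance distortion, not bias built into the design. All sizes rest on the assumed SD, shift and split. The change is worth making because it is cheap and costs almost no power when it turns out to be unnecessary.

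**What to change.** - **Sections 3.3 and 3.5.3:** record the planned procedure before allocation. Stratify the 1:1 randomisation by it (planned resection v planned second biopsy), using a concealed list held away from the recruiting clinicians, with varying block sizes.
- **Sections 1.3 and 5:** replace the plain t-test with a two-factor ANOVA or linear model of PDPN decrease on arm and planned procedure. Use the planned procedure, so that the factor cannot be affected by arm.
- **Section 1.1:** align the secondary and tertiary objectives with section 1.3 on which later specimens count.

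The cost is one degree of freedom (17 instead of 18), a two-stratum list, and some allocation predictability to manage because the administering clinicians know the arm. Incomplete blocks may leave the strata slightly uneven, so the 80% in the table is what exact within-stratum balance would give. No extra patients or procedures are needed.

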Our tertiary endpoint will be measured from the same patient resection or second biopsy material used to measure our secondary endpoint. We will compare the morphology of cells included in the oral lesion to normal oral squamous epithelial cells. Our tertiary endpoint will be met if MASL treated OSCC cells appear less dysplastic than they appeared before treatment. Dysplasia will be graded on a scale of 1 to 5, with 5 being the most dysplastic. Our hypothesis predicts that MASL treated OSCC cells will appear more cuboidal and flatter than they were before treatment.

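### Section 1.3 makes treated-lesion PDPN below normal tissue a necessary condition of success, although the stated aim is only a decrease and no reason for the overshoot is given

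*Protocol*

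**What the plan says.** Protocol section 1.3 states the rule for the secondary endpoint in three parts.

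- Against normal cells: "Our secondary endpoint will be met if MASL treated OSCC cells express less PDPN than normal cells from the same sample specimen".
- Against LECs, joined as an addition: "these OSCC cells will express PDPN levels that are lower than PDPN levels expressed by lymphatic endothelial cells (LECs) from the same specimen".
- Against placebo, again as a requirement: "Our secondary endpoint will also require that the degree of PDPN expression decrease occurring after MASL administration is greater" than any decrease on placebo. For this part only, a test is named: "This comparison will be analyzed by t-test to achieve a p value less than 0.05".

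Entry to the treatment phase (sections 1.3 and 3) requires lesion PDPN above that of normal cells, and equal to or above that of LECs, in the same specimen.

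The aim in section 1.1 reads: "We will determine if MASL treatment can decrease PDPN expression and normalize cell morphology in oral cancers and precancerous lesions". The Study Design Flowchart likewise predicts a reduction in PDPN. The secondary objective in 1.1 is "To evaluate and compare the PDPN expression of cells included in the resected oral lesion to normal oral squamous epithelial cells".

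**The concern.** The three parts are joined, so all must hold. A randomised result that favours MASL at p<0.05 is not enough if treated lesion cells do not also fall below normal tissue. Because every enrolled lesion starts above normal, the rule asks for more than a return to normal. Neither the aim nor the prediction asks for that, and no passage gives a reason for it.

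What is at stake is the verdict on the only endpoint in section 1.3 that has a placebo comparison. Someone who follows the rule exactly could report the endpoint as not met when MASL has done what section 1.1 asks, namely decrease PDPN, and has done so significantly better than placebo.

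**Working it through.** The plan gives no figure for this condition, so there is none to reproduce. The 10 patients per arm and the 40% difference in section 3.3 come without an SD, a power or a defined scale, and the point does not depend on them. The check is a comparison of the passages.

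**Notation.** L0 and L1 are lesion PDPN before and after treatment, N is PDPN in normal cells and E is PDPN in LECs, each compared within its own specimen.

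| | Against normal cells | Against LECs | Against placebo |
|---|---|---|---|
| Entry (1.3, 3) | L0 > N | L0 ≥ E | none |
| Success (1.3) | L1 < N | L1 < E | greater fall, p<0.05 |
| Aim (1.1) and prediction (Flowchart) | no level set | no level set | a decrease on MASL |

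**Step 1: structure.** Success = (L1 < N) and (L1 < E) and (greater fall than placebo, p<0.05). If the first part fails, success fails whatever the t-test shows.

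**Step 2: distance to travel.** Entry gives L0 > N and success needs L1 < N. If the normal-cell level is comparable in the two specimens, the lesion must pass from above N to below it.

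**Step 3: the case that goes wrong.** Suppose the fall on MASL exceeds that on placebo at p<0.05, L1 is below E, and L1 is at or just above N. Two parts hold and the first does not, so the endpoint is not met. This is so whether the condition is judged per patient or on the arm mean. An exact tie matters only if PDPN is read on a coarse scale. On a continuous scale the affected region is L1 at or just above N. Section 1.3 says IHC can serve qualitatively and quantitatively but fixes no scale.

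**Step 4: comparison with the objectives.** The secondary objective asks for a comparison with normal cells and sets no level. The tertiary objective names the same comparator for morphology ("To evaluate and compare the morphology of cells included in the resected oral lesion to normal oral squamous epithelial cells"), yet its endpoint is judged against the pre-treatment state: "Our tertiary endpoint will be met if MASL treated OSCC cells appear less dysplastic than they appeared before treatment". The protocol thus treats improvement from baseline as success for morphology, but not for PDPN.

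**Illustration only.** Let R = L0/N, which the documents do not give. A relative fall f meets the normal-cell condition only if R(1 − f) < 1, that is f > 1 − 1/R:

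- R = 1.5: f must exceed 1 − 1/1.5 = 33%.
- R = 2: f must exceed 1 − 1/2 = 50%.
- R = 3: f must exceed 1 − 1/3 = 67%.

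If the 40% in section 3.3 were read as a relative fall, which the protocol does not say, the condition would hold only for R < 1/0.6 = 1.67. This shows how the rule behaves. It says nothing about where this trial's lesions lie.

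**The case against.** The strongest reply is that the rule is demanding but clear. A stricter threshold in the predicted direction does not contradict a predicted decrease, and under the rule as written a lesion at the normal level is correctly not met. That stands: there is no contradiction here, and a sponsor may set a high bar. What remains is that the bar is unexplained and that the verdict can then depart from the answer to the question in section 1.1.

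A second reply is that the secondary objective names normal epithelium as comparator, so the condition carries the objective into the endpoint. This stands as a reason to keep and report the comparison. It does not require a below-normal threshold. The contrast with the tertiary endpoint is supporting evidence only, since it could equally be called a mismatch on the tertiary side. Nor does anything oblige success to be the mirror image of entry.

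Three stronger readings are tempting and are not supported:

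- A reader might infer that the trial will probably miss this endpoint. With no scale, SD or baseline ratio, no such probability can be given. The chance of passing for a mean placed exactly on a threshold would be the same for any threshold, including the LEC one.
- A reader might fault section 1.3 for not saying whether the condition is judged per patient or on arm means. That may be settled in an SAP that is not at hand.
- A reader might take the protocol's language of normalising as a PDPN target. Where it is used, it refers to morphology.

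**Conclusion.** The point holds as a matter of wording. Section 1.3 makes PDPN below normal tissue necessary for success, the stated aim and prediction need only a decrease, and no reason for the difference is given. A significant advantage over placebo with lesions at or near normal would be declared not met.

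The size is modest. The endpoint is secondary, the between-arm t-test is produced in any case, no other rule in the protocol depends on the endpoint being met, and the error is towards a false negative, not a false claim of effect. The conclusion rests on reading the three parts as jointly required, which the linking words in section 1.3 support, and on no numerical assumption. Confidence is high on the wording. Whether the sponsor intended the overshoot cannot be told from the document. It is a change to consider, not a defect that invalidates the trial.

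**What to change.** In section 1.3, define success on the secondary endpoint by the randomised MASL-versus-placebo comparison of change in OSCC PDPN, using the t-test at p<0.05 already stated. Report the within-specimen comparisons with normal cells (the secondary objective) and with LECs descriptively by arm.

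The LEC part must be dealt with explicitly, because as written it is also necessary: a significant advantage over placebo with lesions still at or above LEC level would be not met as well. If the sponsor wants to keep it as a requirement, section 1.3 should say that success needs both the LEC condition and the placebo comparison, and should drop only the below-normal requirement. If the below-normal requirement is intended, the protocol should give the reason.

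The cost is a change of wording in one section, with no new data and no change to the objectives. The sponsor gives up a more striking definition of success.

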### 3. Research Design and Methods

This trial will be conducted in compliance with the protocol, Good Clinical Practice (GCP), and applicable regulatory requirements. Up to 50 patients with visible oral lesions fitting the clinical criteria for cancerous or precancerous lesions undergoing surgery or biopsy (as part of clinical care) at the NJMS or RSDM oral medicine clinic/Rutgers Dental Associates will be targeted for consideration as participants in this study. This includes patients with oral cancer, proliferative verrucous leukoplakia (PVL), conventional oral leukoplakia (OL), and erythroplakia, plus suspect oral papillomas and oral lichen planus. When the identified oral lesion seems appropriate, patients will be asked to sign an informed consent allowing a portion of the biopsy sample or excised tumor to be utilized for research purposes. These specimens will be transferred directly to [name] at Rowan University-SOM for preparation of cell cultures and other research-related testing.

Oral cancers will be sampled surgically by [name], [name], [name], [name] or [name]. Precancerous lesions will be biopsied surgically by [name]. This work will be performed at the NJMS/RSDM/Rutgers Dental Associates and University Hospital in Newark, NJ. Biopsy will be performed by original surgeon as determined by best care practice. These procedures will have been planned as a matter of course for the patient. Therefore, the patients’ participation in this study should not affect their treatment. The operating surgeon will place a sample of the tissue on wet ice. [name] will receive the tissue from the pathology department after they agree that this tissue is not needed for further

analysis. [name] will be waiting in a room as instructed by the surgeon and pathologist and will package the specimens on wet ice and bring them to his lab according to IATA protocols.

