In addition to the process described above, patients already diagnosed with oral cancer/precancer who present to one of the study clinicians for definitive care may also be enrolled in the study if they consent to participation. In these situations, it is routine to request H&E-stained slides from the original surgical pathology department for review as part of the surgical planning for clinical care. For patients who consent, the study clinician or PI would also request 1-3 unstained specimens for D2-40 staining to determine PDPN expression for research purposes. Patients with OSCC cells that express robust levels of PDPN and meet the eligibility criteria will be considered for treatment phase. The remainder of the protocol remains the same.

MASL and placebo lozenges will be prepared by an approved GMP certified facility by chromatography methods established by [name] as described [57]. Lozenges will be stored at the University Hospital Pharmacy and be hand delivered to the administering doctor by study investigators listed on page 1 in a sealed plastic container labeled with the patients name and ID. This work will be performed at the NJMS/RSDM/Rutgers Dental associates and University Hospital in Newark, NJ. [name], [name], [name], [name], [name] or [name] along with [name] and [name] will perform a general physical evaluation of their respective patients before and after MASL or placebo administration. [name] or [name] will

evaluate patient vital signs including temperature, pulse, blood pressure, and overall health after administration. [name] or [name] will also assist with management of any complication should it arise.

In this approach, MASL will find administration through topical exposure to oral lesions in the mouth as the lozenge dissolves. Patients will be asked to dissolve the lozenge in their mouth for at least 5 minutes before being chewed, and refrain from spitting, eating, or drinking for at least 20 minutes after lozenge administration. Subjects will be asked to finish chewing the lozenge within 20 minutes. Systemic exposure through the blood stream may also be accomplished. Data from university studies on cell lines and animal models indicate that MASL can be applied topically or eaten to target PDPN in order to inhibit tumor cell growth and migration. However, pharmacokinetics of this compound have not been established.

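### The MASL-versus-placebo t-test on PDPN decrease does not adjust for first-biopsy PDPN, which every treated patient already has; adjusting is a cheap and usually modest gain in precision

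*Protocol*

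**What the plan says.** Section 1.3 sets the basis for all endpoints: "Endpoints will be determined by cell morphology and PDPN expression examined by IHC". The secondary endpoint includes the one contrast between arms that has a test attached. PDPN must fall more after MASL than after placebo, and "This comparison will be analyzed by t-test to achieve a p value less than 0.05". The section does not say whether the decrease is absolute or percent, or whether the test is one- or two-sided.

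The other endpoints contain no contrast between arms. The primary endpoint compares lesion with normal cells before treatment. For morphology, "Our tertiary endpoint will be met if MASL treated OSCC cells appear less dysplastic than they appeared before treatment".

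Section 5 lists t-tests and ANOVA in general terms, without tying ANOVA to an endpoint or to the arms. Section 4.2 relates results to age and sex only.

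First-biopsy PDPN is an entry requirement (Section 3): "Robust levels of PDPN will be defined as greater than normal cells and equivalent or greater than PDPN levels expressed by lymphatic endothelial cells". For patients diagnosed elsewhere, the study will "request 1-3 unstained specimens for D2-40 staining to determine PDPN expression for research purposes". On the assay, Section 1.3 says that "it can be used to qualitatively and quantitatively assess PDPN expression".

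Section 3.3 plans up to 10 patients per arm, "based on a difference of 40% with respect to Podoplanin expression and MASL sensitivity".

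**The concern.** The decrease is the first-biopsy value minus the second. Subtracting the whole baseline is the right correction only if the second value tracks the first with a slope of 1. With a lower slope, the change score over-corrects and carries baseline noise into the arm comparison. ANCOVA estimates the slope and removes that noise. With at most 20 treated patients precision is scarce, and the baseline value has to be on file before any decrease can be computed.

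The separate wording point is about Section 3.3. It sizes the trial on two quantities, and only PDPN expression appears in Section 1.3 as a contrast between arms. The reader cannot tell which comparison the 40% belongs to.

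**Working it through.** **The plan's own figure.** The 10 per arm can be neither confirmed nor refuted, because Section 3.3 gives no SD, power, sidedness or scale. For a difference of 40 points and a two-sided 0.05 t-test, 10 per arm has 80% power if the SD of the decrease is about 30 points (detectable standardised difference 1.325; 40 / 1.325 = 30.2) and 90% if it is about 26 points.

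**Inputs.** From the protocol: 10 per arm, 1:1 allocation, alpha 0.05, difference 40, and an eligibility floor at the level of lymphatic endothelial cells (LECs). Assumed:
- The test is two-sided and the decrease is absolute.
- The SD of a single measurement is 30 points before selection.
- The pre/post correlation r before selection is 0.2 to 0.85.
- Baseline is normal with a common cut-off.
- The share of lesions passing the floor is 30%, 50%, 60% or 75%. These shares are borrowed from the Section 2 figures for raised PDPN (over 30% of precancers, over 60% of oral cancers, about 50% of T1/T2 and 75% of T3/T4).

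**Formulas**, in units of the single-measurement variance:
- The floor shrinks the baseline variance to V = 0.535, 0.422, 0.363 and 0.265 when 75%, 60%, 50% and 30% pass (variance of a truncated normal).
- Change-score t-test: (1 - r)² × V + (1 - r²).
- ANCOVA: (1 - r²) × (1 + 1/16). The 1/16 is the average cost of estimating the slope with 20 patients, 1/(20 - 4).

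Example with r = 0.5 and 60% passing: t-test 0.25 × 0.422 + 0.75 = 0.856; ANCOVA 0.75 × 1.0625 = 0.797; ratio 0.931, so 7% less variance.

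**Variance ratio, ANCOVA to t-test**

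| Passing the floor | r = 0.2 | r = 0.5 | r = 0.7 | r = 0.85 | Break-even r |
|---|---|---|---|---|---|
| 75% | 0.783 | 0.902 | 0.971 | 1.018 | 0.79 |
| 60% | 0.829 | 0.931 | 0.989 | 1.027 | 0.74 |
| 50% | 0.855 | 0.948 | 0.998 | 1.032 | 0.71 |
| 30% | 0.903 | 0.976 | 1.015 | 1.040 | 0.62 |

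Setting the two variances equal gives (1 - r) × V = (1 + r)/16, so the break-even is r = (16V - 1)/(16V + 1). Above it, ANCOVA is slightly less precise.

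**Power, t-test to ANCOVA** (noncentral t; 18 df, and 17 df averaged over chance baseline imbalance)

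| Passing the floor | r = 0.2 | r = 0.5 | r = 0.7 |
|---|---|---|---|
| 75% | 69.5% to 79.5% | 85.1% to 88.2% | 96.5% to 96.7% |
| 60% | 72.0% to 79.5% | 86.2% to 88.2% | 96.7% to 96.7% |
| 50% | 73.3% to 79.5% | 86.7% to 88.2% | 96.9% to 96.7% |
| 30% | 75.6% to 79.5% | 87.7% to 88.2% | 97.1% to 96.7% |

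**Percent decrease.** In simulation with 60% passing and an assumed baseline CV of 0.35 to 0.7, the t-test has 78-79%, 88-89% and 97% power at r = 0.2, 0.5 and 0.7. ANCOVA has 79-80%, 88% and 97%. There is no material gain. Type I error, simulated at CV 0.5, was 4.8% to 5.1% for all methods.

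**Section 3.3 against Section 1.3.** Section 1.1 has MASL sensitivity assessed in primary cultures. Section 3 allows "a portion of the biopsy sample or excised tumor to be utilized for research purposes", and Section 4.2 lists growth and migration among the outcome measures. None of these states a comparison by arm.

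**The case against.** The strongest reply is that nothing here is an error. An unadjusted t-test on change is a standard, valid choice in a randomised trial, and covariates are commonly left to a statistical analysis plan, which is not at hand. That stands as to validity. But the protocol does not leave the method open: Section 1.3 names the test, so suggesting a better one at no data cost is fair.

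The second reply is that the gain is small. This largely stands. A reader might infer much larger savings from the textbook ratio (1 + r)/2, which gives 0.60, 0.75 and 0.85 at r = 0.2, 0.5 and 0.7, or a 36% cut at r = 0.2 after the cost of estimating the slope. Those figures assume an unselected baseline. Every treated patient here must reach the LEC level, and that floor shrinks the gain at each correlation examined.

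Third, all the inputs are assumed. The Section 2 shares describe raised PDPN, not LEC equivalence, and the LEC comparison is made within each specimen, so it is not a single cut-off. This also stands; the tables give a range and do not estimate this trial's gain.

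Fourth, if percent decrease was meant, ANCOVA on absolute decrease changes the quantity estimated and brings no material gain. That stands, so the scale has to be settled first.

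On Section 3.3, a reader might infer that the trial was sized on something it does not measure. The documents do not support that: culture assays of response to MASL are planned. What is missing is an endpoint that compares them between arms.

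**Conclusion.** The point holds as a low-cost improvement. The only test tied to MASL versus placebo ignores a baseline that every treated patient has. It would be wrong to infer that the t-test is biased or that its error rate is off; only precision is at stake.

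For absolute decrease with an eligibility floor, the benefit is useful at low pre/post correlation, small at 0.5 and nil at about 0.7. At 0.85 it becomes a 2% to 4% loss of variance efficiency. This rests on the assumed SD, correlation, normal baseline and share passing the floor, and on a quantitative IHC score whose scale the protocol does not define. The case for the change is that the possible gain exceeds the possible loss and no new data are needed.

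The mismatch between Sections 3.3 and 1.3 is real whatever the correlation, but it is a minor matter of wording.

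**What to change.** **Sections 1.3 and 5.** State that PDPN decrease is the absolute change between first and second specimen on the same quantitative IHC scale. Compare the arms by ANCOVA with arm and first-biopsy PDPN in the model, two-sided 0.05, and report the adjusted difference with its 95% CI. With first-biopsy PDPN in the model, taking the decrease or the second-specimen value as outcome gives the same arm difference apart from sign, so the endpoint keeps its meaning on the absolute scale. If the sponsor means percent decrease, the protocol should say so; the argument for this change then largely falls away.

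**Section 3.3.** Tie the 40% to the between-arm PDPN comparison of Section 1.3 and say whether it is absolute or relative. Reconcile the mention of MASL sensitivity with 1.3. Simply deleting it would guess the sponsor's intent; the sponsor should say what role the culture results play.

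**Cost.** Wording in three sections and one residual degree of freedom (18 to 17). There are no extra patients, biopsies or assays. The downside is the slight loss of precision if first and second values are highly correlated.
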